## 1 INTRODUCTION

The purpose of this statistical analysis plan (SAP) is to provide details of the statistical analyses that have been outlined within the protocol for Cohorts 1-4 (ZENITH20-1, ZENITH20-2, ZENITH20-3, ZENITH20-4) of Study SPI-POZ-202 amendment 2. A separate SAP will be developed for the newly initiated Cohorts 5-7 of the study (ZENITH20-5, ZENITH20-6, ZENITH20-7). The scope of this plan includes all efficacy and safety analyses of poziotinib in patients with non-small cell lung cancer (NSCLC) with EGFR or HER2 (ErBB2) exon 20 insertion mutations. The PK analysis will not be covered in this analysis plan.

### 1.1 Study Rationale

Poziotinib is an orally administered, irreversible pan-HER inhibitor with activity against HER1, (ErbB1; EGFR), HER2 (ErbB2), and HER4 (ErbB4), as well as HER receptor mutations. The clinical results and safety profile of poziotinib to date in various studies involving patients with relapsed or refractory solid tumors as either a single agent or as combination therapy, have demonstrated that poziotinib may be a good option for patients harboring these mutations. These data support the expectation that poziotinib will be efficacious and well tolerated in solid tumor patients that overexpress EGFR or HER2 or that harbor mutations in EGFR or HER2.

In HER2 overexpressing tumors, clinical activity was shown in a variety of solid tumors in the Phase 1 studies of poziotinib. Additionally, clinical activity has been shown in a Phase 2 study in EGFR-mutant NSCLC at dose of 16 mg once daily (**NOV120101-202**).

In preclinical studies, consistent with reported clinical data, tumors with exon 20 insertions are resistant to first and second generation tyrosine kinase inhibitors. Preclinical models indicate marked sensitivity of both EGFR and HER2 exon 20 insertion mutations to poziotinib [\[1\]](#).

Based on the promising clinical data and acceptable safety profile from studies in HER2-overexpressed tumors and the preclinical data suggesting activity against EGFR and HER2 exon 20 insertion mutations, a single-center Phase 2 Investigator Initiated Study (IIS-POZ-001) was started to evaluate poziotinib in the patients with NSCLC and EGFR or HER2 exon 20 insertion mutations. The design of SPI-POZ-202 is similar to the IIS and is intended for further evaluation of the efficacy and safety of poziotinib in this NSCLC patient population.

### 1.2 Study Objectives

To evaluate NSCLC patients with EGFR or HER2 exon 20 insertion mutations (including duplication mutations) who are treated with poziotinib:

#### 1.2.1 Primary Objective

- **Objective Response Rate (ORR)**

#### 1.2.2 Secondary Objectives

- **Disease Control Rate (DCR)**
- **Duration of Response (DoR)**
- **Safety and tolerability**

#### 1.2.3 Exploratory Objectives

- **Progression-free Survival (PFS)**

- **Quality of Life (QoL)**

## 2 STUDY OVERVIEW

Patients who are at least 18 years old, have histologically or cytologically confirmed locally advanced NSCLC, are positive for EGFR or HER2 exon 20 insertion mutations (including duplication mutation), have measurable disease as per the Response Evaluation Criteria in Solid Tumors (RECIST, version 1.1 [2]), and meet all other inclusion and exclusion study criteria are eligible for this study.

### 2.1 Study Design and Treatment Plan

This is a Phase 2, open-label, single-arm, multicenter study to evaluate the efficacy and the safety/tolerability of poziotinib in various cohorts. Cohorts 1-4 of the study will enroll up to 174 NSCLC patients previously treated with any systemic therapy (87 patients with EGFR exon 20 insertion mutations and 87 patients with HER2 exon 20 insertion mutations) and up to 140 treatment-naïve NSCLC patients (70 patients with EGFR exon 20 insertion mutations and 70 patients with HER2 exon 20 insertion mutations).

The **Screening** period (**Day -30 to Day -1**) lasts up to approximately 30 days prior to **Cycle 1, Day 1**. Patients must meet all Inclusion/Exclusion Criteria to participate in the study. Eligible patients will provide written Informed Consent prior to undergoing any study procedures.

Each treatment cycle is 28 calendar days in duration. There will be four patient cohorts and eligible patients will be enrolled into each cohort in parallel based on EGFR or HER2 exon 20 mutant status and prior treatment status:

- **Cohort 1:** Previously treated patients with EGFR exon 20 insertion mutation positive metastatic NSCLC
- **Cohort 2:** Previously treated patients with HER2 exon 20 insertion mutation positive metastatic NSCLC
- **Cohort 3:** Treatment naïve patients with EGFR exon 20 insertion mutation positive metastatic NSCLC
- **Cohort 4:** Treatment naïve patients with HER2 exon 20 insertion mutation positive metastatic NSCLC

Toxicity will be assessed based on the grade of the adverse events (AEs) using CTCAE version 4.03.

Poziotinib will be taken orally, once daily (QD) with food and a glass of water at approximately the same time each morning. On **Day 1** of each 28-day cycle, the patient's absolute neutrophil count (ANC) must be  $\geq 1.5 \times 10^9/L$  and platelet count must be  $\geq 100 \times 10^9/L$  before administering poziotinib.

All patients will be treated until 24 months of treatment, disease progression, death, intolerable AEs, or other protocol-specified reason for patient withdrawal.

### 2.2 Study and Treatment Duration

The total duration of the study will be approximately 2 years. However, some patients may receive longer treatment if responding to the treatment. The duration of study participation for each patient, in general, includes the following segments:

- **Screening Period:** up to 30 days
- **Treatment Period:** 28 days per cycle until 24 months of treatment, disease progression, death, intolerable AEs, or other protocol-specified reason for patient withdrawal.
- **Safety Follow-up Visit:** 35 ( $\pm 5$ ) days after the last dose of poziotinib

## 2.3 Tumor Assessments

This section provides general description of tumor assessments. All images acquired at baseline and follow-up will be sent to Bioclinica, Inc. for central radiographic review by an Independent Review Committee (IRC) for response evaluation based on RECIST criteria, Version 1.1 [2]. Details are found in Bioclinica Independent Review Charter for SPI-POZ-202, including a list of all pre-specified modifications from RECIST 1.1 criteria.

Patient eligibility for enrollment will be based on the scans performed before the patient signed the ICF and review by the Site Principal Investigator. After patient enrolled into the study, baseline tumor assessment is required. All baseline and follow-up tumor assessments must be performed using computed tomography (CT), positron emission tomography (PET)/CT, or magnetic resonance imaging (MRI). The baseline tumor assessment must be performed within 2 weeks prior to, or on **Cycle 1, Day 1**. In situation that images are incomplete at baseline evaluation (i.e. missing images from some body sites), the most recently available images of the missing body sites prior to baseline (ie. at Screening) may be sent to Bioclinica as part of baseline evaluation.

For patients with known brain metastases, a baseline brain MRI scan will also be performed to assess the status of brain metastases if present.

Tumor assessments will be performed at

- approximately 4 weeks (**Cycle 2, Day 1**) [ $\pm 7$  days], 8 weeks of treatment (**Cycle 3, Day 1** [ $\pm 14$  days]), and approximately every 8 weeks ( $\pm 14$  days) thereafter [Original Protocol]
- approximately 4 weeks (**Cycle 2, Day 1** [up to **Cycle 2, Day 7**]), 8 weeks (**Cycle 3, Day 1** [up to **Cycle 3, Day 7**, with at least 28 days from previous tumor assessment]), and approximately every 8 weeks ( $\pm 7$  days) thereafter [Amendment 1 & 2]

For each patient, subsequent tumor assessment must use the same radiographic technique performed at baseline, either CT, PET/CT, or MRI. Tumor assessments will be made according to RECIST criteria, Version 1.1 [2] using appropriate radiographic imaging or other techniques. Patient enrollment and clinical decisions will be based on local imaging review and the efficacy assessments for final analysis will be based on the central imaging review by IRC at Bioclinica.

Measurable and non-measurable lesions that will not be followed by radiographic methods should be documented appropriately.

### 2.3.1 Baseline Tumor Assessments

Consistent with RECIST, at baseline tumor assessment, up to 5 measurable lesions (maximum of 2 lesions per organ) representative of all involved organs will be identified as **target lesions**. Target non-nodal tumor lesions (TLs) should have longest diameter  $\geq 10$ mm and can be measured reproducibly. Target lymph nodes (LNs) should have short axis  $\geq 15$ mm. The sum of diameters (SOD), which is the sum of the longest diameter of all target non-nodal lesions and the short axis of all target LNs, will be calculated as the reference baseline value for tumor response evaluation later in the study.

All the other TLs, pathological LNs (short axis  $\geq 10$ mm), and lesions not measurable by CT or MRI will be identified as **non-target lesions** and the size of these lesions are not recorded for the purpose of follow-up.

### 2.3.2 Follow-up Tumor Assessments

**Target lesions** are followed for tumor size, (i.e., longest diameter of TLs and short axis of LNs), and SOD are calculated for response evaluation using RECIST 1.1 criteria. At each tumor assessment, the tumor response of **target lesions** is determined as below.

- **Complete Response (CR):** Disappearance of all non-nodal target lesions and any pathological lymph nodes must have become normal (i.e., decrease in short axis to  $< 10$  mm).
- **Partial Response (PR):** At least a 30% decrease in SOD of target lesions, taking as reference the baseline SOD. Additionally, progression of target lesions must not be present.
- **Progressive Disease (PD):** At least a 20% increase in the SOD of target lesions, taking as reference the nadir SOD (or the baseline, if the baseline is the nadir value). In addition to the relative increase of 20% in SOD, the SOD must also demonstrate an absolute increase of  $\geq 5$  mm.
- **Stable Disease (SD):** Neither sufficient shrinkage of target lesions to qualify for PR, nor sufficient increase to qualify for PD.
- **Not Evaluable (NE):** If  $\geq$  one (1) target lesion is classified as NE for a particular time point, the SOD and percent change cannot be accurately determined and the Target Response will be NE for that time point. The only exception is if the SOD of the evaluable target lesions shows a  $\geq 20\%$  increase from the nadir SOD and an absolute increase of  $\geq 5$  mm. In this case, the Target Response will be PD.
- **Not Applicable (NA):** No target lesions were identified at baseline. Subjects with no target lesions will be evaluated based on the assessment of non-target lesions or the presence of new lesions.

**Non-target lesions** are assessed qualitatively with present, absent or unequivocal progression and tumor response is determined as below.

- **Complete Response (CR):** The nontarget lesion has fully resolved. The lymph node must be nonpathological in size ( $< 10$  mm in the short axis).
- **Non-CR/Non-PD:** Persistence of the non-target lesion.
- **Progressive Disease (PD):** The non-target site of disease has shown unequivocal progression.
- **Not Evaluable (NE):** Any non-target lesion which was present at baseline, but which subsequently became unevaluable.
- **Not Applicable (NA):** No non-target lesions identified at baseline.

**New lesions** are tumor lesions that were not present at baseline. The finding of a new lesion should be unequivocal, and the appearance of new malignant lesions denotes disease progression.

### 2.3.3 Time Point Response at Each Tumor Assessment

As summarized in **Table 1**, the time point response at each follow-up tumor assessment are determined according to the evaluation of target lesions, non-target lesions, and new lesions.

**Table 1 Determination of Time Point Response**

Target Lesions	Non-Target Lesions	New Lesions	Time Point Response
CR	CR or NA	No	CR
CR	Non-CR/Non-PD or NE	No	PR
PR	Any but PD	No	
SD	Any but PD	No	SD
PD	Any	Yes or No	PD
Any	PD	Yes or No	
Any	Any	Yes 	
NE	Any but PD	No	NE
NA	CR	No	CR
NA	Non-CR/Non-PD	No	Non-CR/Non-PD
NA	NE or NA	No	NE

 If the finding of new lesion is equivocal, it should be confirmed at next scan.

## 3 STATISTICAL CONSIDERATIONS

This is a Phase 2, open-label, single-arm, multicenter study with seven patient cohorts and this SAP focuses on the first 4 cohorts. Each cohort is an independent study and will be analyzed separately at different time. For Cohorts 1-4 (ZENITH20-1, ZENITH20-2, ZENITH20-3, ZENITH20-4), all statistical summary tables, data listings, and figures will be produced separately with the corresponding clinical study reports. The statistical analyses and clinical study reports may be submitted to the Agency separately for each cohort.

### 3.1 Randomization

This is a single-arm, non-randomized, independent cohort design study and patients are enrolled into study cohorts based on tumor characteristics.

### 3.2 Sample Size Determination

There are four patient cohorts and each cohort is considered to be a standalone study with individual primary endpoints and powered for testing hypotheses separately. The original justification for the sample size calculation is provided in the protocol and is described below.

The reported response rate of patients with EGFR exon 20 mutations to gefitinib and erlotinib is low at 5% with a median PFS of 1.5 months. A combined post-hoc analysis of LUX-Lung 2, LUX-Lung 3 and LUX-Lung 6 clinical trials showed that the response rate to afatinib is 8.7%

with a median PFS of 2.7 months in EGFR exon 20 mutant patients. In a pivotal study of crizotinib vs. chemotherapy, the response rate of chemotherapy-treated patients with previously treated ALK-positive NSCLC was 20%.

There is no approved treatment available for EGFR exon 20 insertion mutation NSCLC patients. Unlike other EGFR mutations, patients with EGFR exon 20 insertions rarely respond to gefitinib or erlotinib. A review of 84 patients with exon 20 insertion mutations across different series treated with either gefitinib or erlotinib demonstrated an RR of only 11% with a PFS of 2.4 months (Naidoo et al, 2015). Similarly, treatment with afatinib in this patient population is also associated with a low RR and PFS (8.7% and 2.7 months, respectively; (Yang JC et al, 2015). Overall survival of patients with EGFR exon 20 insertion mutations is similar to that of patients without EGFR-mutant NSCLC but inferior to that of patients with EGFR exon 19 deletion or L858R advanced NSCLC (Oxnard GR et al, 2013).

Patients with HER2 mutated NSCLC treated with lapatinib, a pan HER inhibitor, experienced progressive disease. The most promising data to date have been obtained using irreversible TKIs targeting HER2/3 and EGFR, such as afatinib, neratinib and dacomitinib. Three out of eight HER2 mutant NSCLC patients treated with afatinib achieved a partial response. Dacomitinib demonstrated an overall 13% response rate in the 26 HER2-mutant patients.

### 3.2.1 Previously Treated Patients - Cohort 1 and Cohort 2

**Cohort 1** will enroll EGFR exon 20 insertion mutation positive NSCLC patients who have been previously-treated and **Cohort 2** will enroll patients with previously-treated HER2 exon 20 insertion mutation positive NSCLC. The statistical analysis of primary as well as secondary outcomes will be performed separately for each cohort. Each cohort will be a single-arm and the primary test of hypotheses will be based on a single proportion. Based on the literature and per the FDA reviewed protocol, an observed ORR of 30%, with 17% as the lower bound for 95% CI, is considered to be the clinically meaningful efficacy in our study. Sample size calculation is based on single arm hypothesis testing to reject non-desired ORR of 17% vs. clinically meaningful ORR of 30%. A sample size of 87 patients in each cohort will provide 85% power, for a two-sided test with a significant level of 5% to reject a non-desired ORR of 17% if the observed ORR is 30% or higher. A sample size of 87 patients in each cohort will also provide 95% CI that contains 30% and rules out 17%, since the lower bound of the CI is above 17%.

### 3.2.2 Treatment Naïve Patients - Cohort 3 and Cohort 4

Similar to **Cohorts 1** and **2** in previously-treated patients, the study will have 2 additional patient cohorts (**Cohorts 3** and **4**) with no prior treatment for exon 20 mutation positive NSCLC. The statistical analysis of primary as well as secondary endpoints will be performed separately for each cohort. Each cohort will be single-arm and the primary test of hypotheses will be based on a single proportion. Based on the literature and per the FDA reviewed protocol, an ORR of 20% is considered to be the lower threshold of efficacy in our study. Sample size calculation is based on the single arm hypothesis testing to reject non-desired ORR of 20% vs. clinically meaningful ORR of 40% in the study. A sample size of 70 patients in each cohort will provide 90% power, for a two-sided test with a significant level of 5%, to reject a non-desired ORR of 20% if the observed ORR is 40% or higher. A sample size of 70 patients in each cohort will also provide 95% CI that contains 40% and rules out 20% as the lower bound is above 20%.

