#### 3.3.5 Analysis Population

- The **As-Treated Population** will be the primary analysis population and include all patients who receive at least one dose of study medication.
- The **Evaluable Population** consists of all patients who are enrolled, have at least one dose of poziotinib treatment, and is evaluable for tumor response based on RECIST, Version 1.1, by central imaging review. The efficacy data will also be analyzed using the **Evaluable Population**.

The **Evaluable Population** will exclude patients whose best overall response is NE as well as patients who do not have target lesion at baseline, all based on the central imaging review by IRC at Bioclinica.

- The **Safety Analysis Population** includes all patients who signed informed consent, enrolled, and received at least one dose of study treatment. All demographics, baseline characteristics, and safety data will be analyzed using the **Safety Analysis Population**.

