### 3.4 Futility Analysis

The study includes a futility analysis to be conducted in each patient cohort when the response rate for the first 20 patients in that cohort is available. A patient cohort will be stopped for futility if the ORR is <10%. No adjustment to multiplicity will be made for the futility analysis.

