## 5.2 Primary Endpoint

### 5.2.1 Objective Response Rate (ORR)

The primary endpoint is ORR and is defined as the proportion of patients whose best overall response is confirmed to be CR or PR from the first dose of poziotinib until the last tumor assessment on study. The unconfirmed ORR, which does not require confirmation scans for CR/PR, will also be provided.

ORR and unconfirmed ORR will be estimated with count, percentage and 95% CI (Clopper-Pearson).

The test of hypothesis of the primary endpoint will be performed using the 95% CI. The prespecified primary endpoint criteria for each cohort is stated in [Section 3.2](#).

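### With the Clopper-Pearson rule that decides the primary endpoint, 87 patients give Cohorts 1 and 2 about 80% power, not the stated 85%

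*SAP*

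**What the plan says.** Section 3.2.1 bases the sample size of Cohorts 1 and 2 on "single arm hypothesis testing to reject non-desired ORR of 17% vs. clinically meaningful ORR of 30" per cent, and gives the result as "A sample size of 87 patients in each cohort will provide 85% power, for a two-sided test with a significant level of 5" per cent. It attaches this power to the observed ORR being 30% or higher. It adds that the interval from 87 patients "rules out 17%, since the lower bound of the CI is above 17" per cent. It does not name the test or formula behind the 85%.

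Section 5.2.1 fixes the analysis: "ORR and unconfirmed ORR will be estimated with count, percentage and 95% CI (Clopper-Pearson"), followed by "The test of hypothesis of the primary endpoint will be performed using the 95% CI". For the threshold it points back: "The prespecified primary endpoint criteria for each cohort is stated in" Section 3.2. No other primary test is named.

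Section 3.3.5 sets the denominator: the As-Treated Population "will be the primary analysis population and include all patients who receive at least one dose of study medication".

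**The concern.** Read together, the two sections define the decision rule completely: success if the Clopper-Pearson lower 95% bound exceeds 17%. That rule has one exact power at n = 87, and the SAP's figure should match it. An exact interval is more demanding than the normal approximation commonly used for planning, so the stated figure may belong to a test that will not be used.

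At stake is the stated chance of success on the primary endpoint in two cohorts that Section 3.2 treats as standalone, separately powered studies. The borderline result also depends on it: the SAP never states the responder count that separates success from failure, and the two calculations disagree about 22 of 87.

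**Working it through.** **Inputs.** n = 87, p0 = 0.17, p1 = 0.30, two-sided 5% (Section 3.2.1); Clopper-Pearson 95% interval as the test (Section 5.2.1); all treated patients as the denominator (Section 3.3.5).

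**1. The plan's own figure.** One-sample normal-approximation test, null variance for the critical value, no continuity correction:

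Power = Φ{ [p1 − p0 − 1.96·√(p0(1−p0)/n)] / √(p1(1−p1)/n) }

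- √(0.17 × 0.83/87) = 0.04027, times 1.96 = 0.0789
- √(0.30 × 0.70/87) = 0.04913
- (0.13 − 0.0789)/0.04913 = 1.04; Φ(1.04) = 85.07%

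The same formula solved for 85% power gives n = 86.8, hence 87. This is evidently the source of both figures.

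**2. The cut-off under the SAP's rule.** The Clopper-Pearson lower bound for x responders is the 2.5% quantile of Beta(x, n − x + 1).

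| Responders | Observed ORR | Lower bound | Above 17%? |
|---|---|---|---|
| 22/87 | 25.3% | 16.58% | no |
| 23/87 | 26.4% | 17.55% | yes |
| 26/87 | 29.9% | 20.54% | yes |

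Success needs at least 23 responders.

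**3. Exact power and size, X ~ Binomial(87, p).**

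| Rule | Power at 30% | Upper-tail error at 17% |
|---|---|---|
| X ≥ 22 | 85.98% | 3.23% |
| X ≥ 23 (the SAP's rule) | 79.89% | 1.76% |

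The approximation in step 1 puts the critical value at 0.17 + 0.0789 = 24.9%, or 21.7 responders, so it counts 22 as a success. The SAP's interval does not, and the 22-responder rule would exceed the 2.5% upper-tail limit.

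**4. Related quantities.**
- Shortfall: 85 − 79.9 = 5.1 percentage points. Type II error: 100 − 79.9 = 20.1% against the implied 15%; 20.1/15 = 1.34.
- With n = 87 and the 23-responder cut-off, 85% power is reached at a true ORR of about 31.0%.
- Section 3.4: "A patient cohort will be stopped for futility if the ORR is <10" per cent, meaning 0 or 1 responder in the first 20. If that stop is binding, power at 30% is 79.6%.

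**5. Cohorts 3 and 4** (n = 70, 20% against 40%). 21/70 has a lower bound of 19.62% and fails; 22/70 has 20.85% and succeeds. P(X ≥ 22 | 0.40) = 94.5%, so the stated 90% is met.

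**The case against.** The strongest defence is that 85% is not a slip. It is the correct normal-approximation power, Section 3.2.1 never says it is Clopper-Pearson power, and planning by approximation while analysing with an exact interval is common and conservative. This stands as far as it goes: the arithmetic is right for its formula, and false positives are controlled at 1.76%. But the SAP names no approximation and presents 85% as what the cohort delivers, and the only test it specifies delivers 79.9%.

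Exact power also moves in a sawtooth with n. Under the same rule it is 81.0% at n = 84, 75.9% at 85, 83.4% at 89 and 78.8% at 90. This is a reason not to over-read single points, but all four values are below 85%.

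Section 3.2 says it repeats the protocol's original justification, so overwriting the figure in the SAP alone could make the two documents disagree. That is a fair point about how to make the correction. The 85% can stay as the planning figure if its method is named and the exact power is given beside it.

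A fixed count of 23 holds only at n = 87. If 90 patients were treated, 23 responders would give a lower bound of 16.94% and fail. The binding rule should therefore remain the lower bound, with the count tied to n = 87.

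Finally, Section 3.2.1 also calls an observed ORR of 30% with a lower bound of 17% clinically meaningful. If an observed 30% were also required for success (27/87), power would be about 46%. Section 5.2.1, however, makes the test through the interval alone, so the sentence is better read as describing clinical relevance. It does not support 85% under either reading.

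**Conclusion.** The concern holds. Under the decision rule written in the SAP, 87 patients give 79.9% power at a true ORR of 30%, 5.1 points below the stated 85%. This takes exactly 87 treated patients, independent binomial responses, success defined as a Clopper-Pearson lower 95% bound above 17%, and no further requirement on the observed ORR.

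The fault is a mismatch between the planning formula and the analysis rule. It affects the stated power of Cohorts 1 and 2 only; the validity of the test and the power claim for Cohorts 3 and 4 are not in question.

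A related wording fault appears in the power sentences of both Sections 3.2.1 and 3.2.2: power is attached to the observed ORR. Power is defined at the true ORR. Under the SAP's rule an observed ORR at or above the target always succeeds, so the sentences as written have no power to state.

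**What to change.** In Section 3.2.1, replace the power statement by one to this effect: with 87 treated patients, the exact power to reject an ORR of 17% through the 95% Clopper-Pearson interval is about 80% if the true ORR is 30%; at this sample size, success corresponds to at least 23 responders (26.4%). If the 85% is kept for continuity with the protocol, label it as the normal-approximation planning figure and put the exact power next to it.

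Keep the lower bound above 17% as the rule, so that the cut-off is recalculated if the number treated differs from 87. Say in one clause that the observed 30% describes clinical relevance and is not an additional success criterion, if that is what is meant.

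Change the observed ORR to the true ORR in the power sentences of Sections 3.2.1 and 3.2.2. Adding the matching figures for Cohorts 3 and 4 (at least 22 of 70, 94.5% exact power at 40%) would be consistent but is optional.

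The cost is a few sentences in the SAP and one less favourable number. Sample size, test, significance level and trial conduct stay as they are.

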### 3.3 Statistical Principles

#### 3.3.1 General Principles of Analysis

The statistical analyses will be reported using summary tables, figures, and data listings. All analyses and tabulations will be performed using SAS® Version 9.3 or higher. All tables, listings, and figures will be validated and reviewed before being finalized.

In summary tables of continuous variables, the minimum and maximum will be presented to the same number of decimal places as the original data. The mean, median, standard deviation (SD), standard error (SE), and 95% confidence interval (CI) will be presented to one more decimal place than the original data.

In summary tables of categorical variables, count and percentage will be provided. In general, percentage values are to be presented to whole number if sample size  $\leq 100$ ; to one decimal place if sample size is between 100 and 1000; and to two decimal places if sample size is greater than 1000. Any test of comparison performed will be 2-sided at 5% level of significance unless otherwise specified.

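### Cohorts 3 and 4: the stated 90% power for 70 patients does not follow from the stated two-sided 5% test, whose exact power is 94.5%

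*SAP*

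**What the plan says.** SAP section 3.2.2 sizes Cohorts 3 and 4 separately. The hypotheses are to "reject non-desired ORR of 20% vs. clinically meaningful ORR of 40% in the study", and "Each cohort will be single-arm and the primary test of hypotheses will be based on a single proportion". The claim is "A sample size of 70 patients in each cohort will provide 90% power, for a two-sided test with a significant level of 5" per cent. The paragraph gives no attrition allowance and attaches the 90% directly to the 70 patients. It adds that a 95% CI from 70 patients would contain 40% and exclude 20%.

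The rest of the SAP agrees on the level of the test. Section 5.2.1 says "The test of hypothesis of the primary endpoint will be performed using the 95% CI" and names the interval: "ORR and unconfirmed ORR will be estimated with count, percentage and 95% CI (Clopper-Pearson"). Section 3.3.1 sets the default: "Any test of comparison performed will be 2-sided at 5% level of significance unless otherwise specified". Section 3.3.5 makes all patients with at least one dose the primary analysis population.

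The neighbouring section 3.2.1 makes a claim of the same form for Cohorts 1 and 2: 87 patients, 85% power, two-sided 5%, 17% against 30%.

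**The concern.** Null rate, alternative rate, sample size, alpha and decision rule are all given, so the power is determined up to the choice of method. The stated figure looks too low for a 20-point difference with 70 patients at 5%. Section 3.2 treats each cohort as a stand-alone study powered for its own hypothesis, so the figure is a design property of two of the four. It tells a reader how surprising a failed cohort would be if the true ORR were 40%. If the type II error is about half of what the plan implies, a failed Cohort 3 or 4 counts somewhat more strongly against 40% than the plan suggests.

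**Working it through.** **Inputs.** From section 3.2.2: n = 70, p0 = 0.20, p1 = 0.40, two-sided 5%, stated power 90%. From section 5.2.1: 95% Clopper-Pearson interval, with success when the lower limit is above 20%. From section 3.2.1, as a benchmark: n = 87, p0 = 0.17, p1 = 0.30, two-sided 5%, stated power 85%. The SAP words power in terms of an observed ORR; I read it as the true ORR, since an observed 40% (28/70, lower limit 28.5%) would always succeed.

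**Step 1: reproduce the Cohort 1 and 2 figure.** One-sample normal formula:

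power = Φ{[√n (p1 − p0) − z √(p0 q0)] / √(p1 q1)}, with z = 1.96.

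n = 87: [9.327 × 0.13 − 1.96 × 0.3756] / 0.4583 = (1.2126 − 0.7362) / 0.4583 = 1.039. Φ(1.039) = 85.1%, which matches the stated 85%.

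**Step 2: the same formula for Cohorts 3 and 4.**

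n = 70: [8.367 × 0.20 − 1.96 × 0.40] / 0.4899 = (1.6733 − 0.7840) / 0.4899 = 1.815. Φ(1.815) = 96.5%, against the stated 90%.

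Inverted for 90% power: n = (1.96 × 0.40 + 1.282 × 0.4899)² / 0.20² = 49.8, so 50 patients.

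**Step 3: the rule the SAP specifies.** Clopper-Pearson 95% lower limits with n = 70:

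| Responders | Observed ORR | Lower limit | Above 20%? |
|---|---|---|---|
| 21 | 30.0% | 19.6% | no |
| 22 | 31.4% | 20.9% | yes |

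Success therefore needs X ≥ 22, where X ~ Binomial(70, p):

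- P(X ≥ 22 given p = 0.20) = 0.0159, the one-sided type I error.
- P(X ≥ 22 given p = 0.40) = 0.9454, the power. Type II error is 1 − 0.9454 = 5.5%.
- P(X ≥ 22 given p = 0.38) = 0.897, so 90% power belongs to a true ORR of about 38%.

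Under this rule power first passes 90% at n = 56 (18 responders needed, 91.1%) and stays above it from n = 59 (19 needed, 91.4%).

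**Step 4: does another method give 90%?** At n = 70 and two-sided 5%:

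| Method | Power |
|---|---|
| Alternative-variance (Wald) formula | 92.7% |
| Exact Clopper-Pearson rule | 94.5% |
| Normal, continuity-corrected | 95.5% |
| Arcsine | 95.9% |
| Normal formula (steps 1 and 2) | 96.5% |
| Null-variance formula | 98.7% |

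None gives 90%.

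**Step 5: the futility stop.** Section 3.4 stops a cohort at 0 or 1 responder in the first 20. At a true ORR of 40% that has probability 0.05%, and it lowers the exact power only from 0.9454 to 0.9452. It does not explain the gap.

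**The case against.** The strongest defence is that the sentence is true as a minimum: 70 patients do give at least 90% power, the cohorts are not underpowered, and type I error is controlled. That stands, and it limits the weight of the point. It does not make the figure right, because the text states 90% rather than a floor, and the parallel Cohort 1 and 2 figure matches its formula closely.

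A second defence is that 70 may include an attrition allowance. The exact n of 59 with 15% loss gives 59/0.85 = 69.4, so 70; the Wald n of 63 with 10% loss gives 63/0.90 = 70. This is possible, and section 3.2 says the original justification is in the protocol, which is not at hand. But the SAP mentions no allowance and ties the 90% to 70 patients.

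A reader might infer something stronger: that the design was really a two-sided 1% test, because the normal formula gives 90.5% at n = 70 with that level. The SAP does not support this. Under its own exact rule, power is 86.4% at two-sided 1% (24/70 needed) and 91.1% at 2% (23/70 needed), so 1% is not singled out. The SAP nowhere mentions a 1% test, and three sections agree on 5% or a 95% interval. It follows that the outcome at 22 or 23 responders is not in doubt: both are successes under the written rule, and there is no case for a 99% interval.

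**Conclusion.** The stated power for Cohorts 3 and 4 is wrong for the test the SAP describes. It should be about 94.5% by the specified exact rule (96.5% by the normal formula), against the stated 90%, a difference of about 4.5 points. The type II error is 5.5% rather than 10%.

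The error is conservative. Sample size, endpoint, population, interval method and success rule all stand, and no estimate or conclusion changes. The one practical consequence is modest: a failed cohort is somewhat stronger evidence against a true ORR of 40% than the plan implies, and such a result would in any case be read mainly from its observed ORR and interval.

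The verdict rests on three assumptions: that power refers to the true ORR, that all 70 patients are in the denominator, and that success means a 95% Clopper-Pearson lower limit above 20%. Where the pairing of 70 with 90% came from, whether another alpha or an attrition allowance, cannot be told from the SAP.

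**What to change.** Keep 70 patients per cohort and the 95% Clopper-Pearson rule, and correct the power sentence in section 3.2.2. Suggested wording: With 70 patients, the lower limit of the 95% Clopper-Pearson interval exceeds 20% when at least 22 patients (31.4%) respond; exact power is 94.5% if the true ORR is 40% (about 90% if it is 38%), with a one-sided type I error of 1.6%.

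Alternatively, if 70 came from another method or from an attrition allowance, state it, together with the number of patients to which the 90% applies.

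Either way the cost is one sentence in the SAP, with no change to enrolment, data collection or analysis.
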